15	DATA HANDLING AND RECORD KEEPING.....	35
15.1	Data Collection and Management Responsibilities	35
15.2	Protocol Deviations.....	36
15.3	Study Closure	36
15.4	Study Records Retention.....	36
16	APPENDICES	37
	Appendix A: ECOG Performance Status.....	37
	Appendix B: Reportable Events	38
	Adverse Event (AE) Definition	38
	Serious Adverse Event (SAE) Definition	38
	Unanticipated Problem 39	
	Suspected Adverse Reaction.....	39
	Expectedness and Attribution	39
	Expectedness 39	
	Attribution 40	
	Adverse Event Monitoring 40	
	Appendix C: Clavien-Dindo Classification for Surgical Complications.....	42
	Appendix D: Examples of Grading Using Clavien-Dindo Classification	43
	Appendix E: Wound Healing Assessment - GTSD Training Manual- Pages 246-248	44
17	LITERATURE REFERENCES.....	47

SCHEMATIC OF STUDY DESIGN

**Pre-Operative Immuno-Modulatory SBRT
(POIMS Trial)
A pilot trial in early stage NSCLC**

PROTOCOL SUMMARY

Title	Pre-Operative Immuno-Modulatory SBRT (POIMS Trial): A pilot trial in early stage NSCLC
Protocol Number	IIT-2020-POIMS-Lung
Phase	Pilot
Design	Single arm pilot trial
Study Duration	
Approximately 5 years
 
 • Enrollment Period – approximately 18 months • Follow up period for adverse events to 36 months after surgery • Follow up period for post-operative surgical complication / wound healing events- 3-6 months after surgery • Follow-up period for disease outcome–36 months after surgery
Study Center	University of Kansas Cancer Center
Objectives	
Primary: Assess the impact of non-ablative SBRT (800 cGy X 3 fractions) on immunomodulation in NSCLC tumor cells
 
Secondary: Assess the impact of non-ablative SBRT (800 cGy X 3 fractions) prior to surgical resection on peri- and post-operative surgical complication rate, wound healing, and disease outcomes.

Number of Participants	10
Diagnosis and Main Inclusion Criteria	
Inclusion Criteria:
 
 • Stage I-II NSCLC • Adequate diagnostic biopsy tissue to allow pre-SBRT tumor analysis • Candidate for oncologic surgery (lobectomy or sub lobar resection) for the lung cancer • Lesion located peripherally, ≥ 2 cm from bronchial margin, and 1 cm from visceral pleura, with location deemed acceptable by cardio-thoracic surgeon for resection. • Adequate pulmonary function test results 
Exclusion Criteria:
 
 • Prior history of lung/chest wall surgery • Prior chest radiation • Prior immunotherapy • History of autoimmune disease • Currently using immunosuppressive drugs
Study Product(s), Dose, Route, Regimen	SBRT 800 cGy x 3 fractions

Duration of Administration
	
Total: 4-5 days
 
1-2 days - consultation and simulation
 
3 treatment (study intervention) days
 
Study intervention (SBRT) delivery will be scheduled for 3 consecutive days, but may be modified as needed by the treating radiation oncologist.

Interim Monitoring
	
The data safety monitoring committee (DSMC) of The University of Kansas Cancer Center is responsible for monitoring participant safety for this trial.

Statistical Methodology
	
We will summarize peri- and post- operative surgical complication rates as well as tumor control outcomes using descriptive statistics.
 
Peri- and post- operative surgical complication rates will be quantified using the Clavien-Dindo classification of surgical complications ^{1,2}.
 
Wound healing complication rates will be scaled as defined by the General Thoracic Surgery Database. ³

Stopping Rules
	
If a participant experiences one or more of the following events, possibly related to study intervention, study will be suspended pending DSMC review to determine if study should continue.
 
 a. Wound healing delay beyond standard timeframe as deemed by study Cardio-Vascular (CV) surgeons b. Peri operative/post-operative surgical complications beyond acceptable institutional rates as determined by study CV surgeons c. Death from study intervention

1 INTRODUCTION

1.1 Background

Recent advances in immunotherapy has resulted in a new era for the treatment of NSCLC. Radiotherapy is commonly used in early stage, locally advanced and advanced stage of NSCLC treatment. More recently the utility of highly conformal, large fraction size radiation defined as SBRT has become standard of care for early stage and oligometastatic NSCLC. The interplay of XRT and immunotherapy, however, remains poorly defined in NSCLC.⁴ The immunomodulatory potential of XRT has been long recognized but not yet well defined for clinical utility and integration into combined immunotherapy and XRT regimens. The phenotypic changes in tumor cell surface marker expression (e.g. PD-L1), tumor and surrounding normal tissue microenvironment, and serum/blood immune profile changes due to XRT have not been well elucidated in this patient population. This has been challenging in patients with NSCLC who receive radiation due the difficulty in obtaining post XRT tumor tissue.⁵ Defining the independent effect of XRT, more specifically, SBRT on the immunoregulatory pathways is also complicated by the multitude of trials that combine various immunotherapy agents with XRT complicating the analysis. The impact of the immunomodulation by non-ablative lower dose SBRT prior to definitive surgery on immunoregulatory pathways needs to be defined.^{6,7}

Cell culture and animal data have demonstrated that cytotoxic doses of XRT may not elicit a clinically meaningful alteration in the immune profile. In contrast, several cell culture and animal model studies have indicated that fractionated low dose XRT may provide a more immunomodulatory effect.^{8,9,10} In addition, there is a lack of consensus regarding the superiority of single fraction versus multi-fraction SBRT yielding greater immunomodulation.^{11,12} Studies using an animal model have concluded a fractionated regimen induces a greater abscopal effect than single dose radiation. Furthermore, they showed a regimen of 800 cGy X 3 fractions yielded the most significant changes in the immune profile compared to 2000 cGy X 1 or 600 cGy X 5.¹³ Clinical trials combining radiation with a multitude of immunotherapeutic agents are difficult to interpret due to variations in the trial design, including the specification of the irradiated site, dose/fractionation regimens, scheduling and sequencing differences, selection of the immunotherapeutic agent, and vast disparity in patient/disease selection criteria. The *in vivo* phenotypic changes in tumor cell surface marker expression, tumor and normal tissue microenvironment and gene expression profiles, serum/blood immune profile changes, and circulating tumor cell immunophenotypic and gene expression alterations of non-ablative low dose radiation fractionated SBRT in patients with early stage NSCLC has not been elucidated. Based on published literature, we believe that this proposed trial, using non-ablative SBRT prior to surgery, will be safe. Recent work from the Netherlands reported the results of a systemic review of seven retrospective case series on salvage surgery after local recurrence in patients who had definitive treatment with SBRT. They noted acceptable morbidity and mortality in appropriately selected patients.¹⁴ A recent prospective trial of ablative SBRT performed 10 weeks before surgery noted no perioperative mortality and reported Grade 3 or 4 toxicity in 7 of 40 patients.¹⁵

1.2 Rationale

The current proposal is structured as a pilot trial to evaluate the impact of non-ablative SBRT (800 cGy X 3 fractions) as an immunomodulatory mechanism in patients with early stage NSCLC who are surgical candidates. Tumor, normal tissue and blood specimens will be analyzed for immunomodulatory changes including phenotypic changes in tumor cell surface marker expression, tumor and normal tissue microenvironment and gene expression profiles, serum/blood immune profile changes, and circulating tumor cell immunophenotypic and gene expression alterations.

Published literature showed that cytotoxic doses of XRT may not elicit a clinically meaningful alteration in the immune profile. Further, studies using an animal model have concluded a fractionated regimen induces a greater abscopal effect than single dose radiation. Furthermore, they showed a regimen of 800 cGy X 3 fractions yielded the most significant changes in the immune profile compared to 2000 cGy X 1 or 600 cGy X 5.¹⁶

The immune response within the tumor milieu is a complex dynamic process with an interplay among lymphocyte subsets, antigen presenting cells/dendritic cells, macrophages, and tumor cells. The interactions between the various components is orchestrated by a variety of extracellular and intracellular signaling pathways involving ligand and cell surface expression, cytokine release, and activation or inhibition of a variety of T cell subsets. In order to comprehensively define the immunomodulatory effect of three fractions of 800 cGy on the primary tumor, we will analyze the following: tumor cell surface phenotype, tumor microenvironment immune profile and gene expression profile, T cell repertoire changes in tumor tissue and peripheral blood, and circulating tumor cell phenotype and gene expression profiles. Each of these components has been shown to be impacted by radiation in either a cell culture or animal model systems. By characterizing, quantitating and defining these changes related to three fractions of 800 cGy, it will directly provide important insights to inform rational uses of XRT and immunotherapy in the future.

1.3 Risk/Benefit Assessment

1.3.1 KNOWN POTENTIAL RISKS

Immediate Risks	Wound healing problems, increase in peri-operative bleeding, bronchopleural fistula, prolonged air leak, conversion to open procedure, and/or infection.
Other Risks	Inconvenience to participant due to additional study-related visits (in addition to standard of care visits): 1 screening/enrollment visit, 1 simulation visit and 3 SBRT treatments.

1.3.2 KNOWN POTENTIAL BENEFITS

Long-Range Potential Benefits	Improved disease free survival
--------------------------------------	--------------------------------

1.3.3 Assessment of Potential Risks and Benefits

Rationale for necessity of exposing participants to risks	Potential for improved disease free survival Improve understanding of radiation-mediated immuno modulation of cancer cells in the tumor microenvironment
Justification why benefits outweigh risks	This study can lead to an improvement in cancer control and will improve our understanding of radiation-related cancer biology. The delivered radiation dose (800 x 3) is known to be safe and well-tolerated, and in fact is significantly below the most common SBRT dose regimen used for NSCLC (1800-2000 x 3). Therefore, the investigators believe the risks to the patients are minimized.

Therefore, the potential benefit of this study is judged to outweigh risk and the risk/benefit ratio is in favor of benefit.

1.4 Measures to Minimize Bias: Randomization and Blinding

This study is not randomized or blinded. Consecutive participants will be enrolled to avoid bias.

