2 HYPOTHESIS

Primary: Non-ablative SBRT (800 cGy X 3 fractions) given 5-7 days preoperatively in selected patients with stage I-II NSCLC will result in alterations in the tumor immunoprofile, tumor microenvironment, gene expression profiles and peripheral blood immune repertoire.

Secondary: This regimen will be well tolerated, associated with minimal toxicity, and will not impact on wound healing.

It should be noted that this is designed as a pilot trial, so statistical analysis will be descriptive and formal hypothesis-testing will not be performed

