3 OBJECTIVES AND ENDPOINTS

3.1 Primary Objective

Assess the impact of non-ablative SBRT (800 cGy X 3 fractions) on immunomodulation in NSCLC tumor cells through analysis of targeted cell surface, tumor immune microenvironment, gene expression profile, radiation mediated changes in T-cell repertoire in tumor tissue and peripheral blood and circulating tumor cell surface expression.

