3.3 Primary Endpoints

What is being measured	Measurement time frame	Measurement Tool

The impact of non-ablative SBRT on Immunomodulation in tumor cells
 
Pre and post study intervention biopsy tissue comparison of immunomodulatory parameters including but not limited to PDL1, PDL2, HCA2, IDO, HC10, B2m, Calreticulin, MHC-1, Fas, ICAM
	
From time of consent and collection of archival tumor tissue to time of surgery with collection of post-study intervention tumor tissue.
	
Techniques anticipated include but are not limited to: Immunohistochemistry, Targeted Nanostring (PanCancer ImmunoOncology 360; PanCancer Progression Panel), CTC Isolation, Tumor tissue and peripheral blood T-cell repertoire

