10 TRANSLATIONAL STUDIES

1. Targeted Cell Surface Analysis

Radiation can alter the cell surface expression of many immunomodulatory proteins. Upregulation of PDL1 and PDL2 has been demonstrated in multiple cell lines. Altered expression of MHC 1 on tumor cells has also been reported. Changes in the composition of the immune regulatory cells within the tumor micro-environment in response to changes in tumor cell phenotype has also been demonstrated. Utilizing paired pre-XRT (biopsy) and post XRT (surgical specimen) tumor tissues and normal tissue samples from the resection sample, we will use immunohistochemistry to assess cell surface markers and immune parameters. Tumor panels will include PDL1, PDL2, HCA2, IDO, HC10, B2m, Calreticulin, MHC-1, Fas, ICAM. T-cell panels will include CD3, CD8, FoxP3, TBet, Ki67, GranzymeB; and CD3, CD8, PD1, 1263 Tim3, Lag3, GranzymeB.

2. Tumor Immune Microenvironment

Using the “biopsy-XRT-resection” approach, we will be able to gain insight into the composition of the tumor immune microenvironment before SBRT and understand how SBRT influences the microenvironment and expression of immunotherapy targets. Prior rodent studies have delineated how radiation dose and fractionation can alter the STING pathway.^{23, 24, 25} The consequence of this is recruitment and activation of dendritic cells which can prime CD8+ T cells and mediate a systemic cytotoxic tumor response.²⁶ Similarly, other groups have utilized murine models to delineate how radiation can increase the CD8/CD4 ratio and broaden the T-cell repertoire (Ko et al IJROBP 2019).²⁷ We propose to examine changes in the tumor immune microenvironment focusing on transcriptomic changes as well as functional changes in the T-cell receptor repertoire.

3. Gene Expression Profile

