Circulating tumor cells (CTCs) have been widely used for diagnostic purposes as well as a biomarker to screen for treatment failure. Furthermore, CTCs have been shown to prognosticate both lung and head/neck squamous cell carcinoma patient disease-free survival and contribute to both loco-regional and distant metastasis.^{28,29,30,31} In our model system, we have previously demonstrated that radiotherapy can induce accelerated tumor repopulation in vivo and this is likely regulated by epithelial-to-mesenchymal transition (EMT).^{32,33} Predictably, generation of “mesenchymal” CTCs require EMT and those CTCs with persistent EMT pathway activation have been correlated as a poor patient prognostic outcome particularly in head and neck cancer.^{34,35} In addition, EMT gene expression in CTC’s from lung cancer patients who undergo curative surgical resection have been shown to be a poor prognostic feature.³⁶ Furthermore, PD-L1 expression (and other immunomodulatory proteins) are known to be upregulated in pre-clinical models^{37,38} following radiotherapy and immune cell surface proteins (i.e. PD-L1) has been shown to be expressed in CTCs.³⁹

We propose to examine CTC before and after SBRT. Both mesenchymal and nonmesenchymal (epithelial) expressing CTCs will be isolated from whole blood using specialized nanofabricated cell isolation chips (KU Lawrence collaboration, [name], [name]) designed for harvesting CTCs and demonstrate a 10-100x higher cell capture rate compared with commercial vendors.⁴⁰ Endpoints include mesenchymal and epithelial CTC cell enumeration before and after SBRT; examination of PD-L1 cell surface expression in CTCs; as well as targeted transcriptomic analysis of collected CTCs using a modified Nanostring nCounter® PanCancer Progression Panel customized with supplemental user-defined genes focusing on p38-MAPK pathway.

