We hypothesize from this work that following SBRT there will be a higher proportion of mesenchymal CTCs over epithelial CTCs and these results will be confirmed using targeted transcriptomic analysis. We also anticipate that patients receiving SBRT will have upregulation of PDL1 cell surface expression and will be confirmed by immunofluorescence. We also hypothesize that genes in the p38-MAPK pathway will be upregulated following SBRT and promising genes candidates will be confirmed by immunohistochemistry looking at tumor tissue before and after SBRT. The goal of this work will be to: 1) explore the effect of SBRT on mesenchymal CTC generation; 2) examine the gene expression profile of CTCs with a focus on EMT; and 3) identify promising novel targets within the MAPK pathway that are up-regulated following SBRT that maybe relevant and targetable for metastasis.

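### Section 1.4 offers no protection against measurement bias: the protocol provides no masking to time point for the reader-dependent primary readouts, although coding samples would be cheap

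*Protocol*

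**What the plan says.** Section 1.4 of the protocol, on randomization and blinding as measures against bias, consists of two sentences: "This study is not randomized or blinded. Consecutive participants will be enrolled to avoid bias". It makes no exception for laboratory reading.

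The primary objective (section 3.1) includes "radiation mediated changes in T-cell repertoire in tumor tissue and peripheral blood and circulating tumor cell surface expression". The primary endpoint (section 3.3) compares tissue before and after the intervention on a list of markers, and its tools begin: "Techniques anticipated include but are not limited to: Immunohistochemistry, Targeted Nanostring". CTC isolation and T-cell repertoire are also named there.

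Section 10 adds detail. For paired tissue, "we will use immunohistochemistry to assess cell surface markers and immune parameters". For blood, "Endpoints include mesenchymal and epithelial CTC cell enumeration before and after SBRT; examination of PD-L1 cell surface expression in CTCs". It also commits to directions: "We hypothesize from this work that following SBRT there will be a higher proportion of mesenchymal CTCs over epithelial CTCs", PD-L1 surface expression up with immunofluorescence as confirmation, and p38-MAPK genes up with immunohistochemistry on tissue as confirmation.

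The protocol summary sets the number of participants at 10, and section 2 says that "statistical analysis will be descriptive and formal hypothesis-testing will not be performed". Participant ID numbers appear in section 13.4 for confidentiality only. Sections 8.1, 8.2 and 9.1 refer sample processing, transfer and specimen details to a laboratory manual that is not among the documents.

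**The concern.** The primary comparison is within a person, before against after SBRT, with no control arm. Selection is not the main threat to such a comparison. The main threat is anything that makes the second reading differ from the first for reasons other than treatment. A reader who knows which sample is post-SBRT, and which way it is expected to move, can resolve borderline cells or staining intensities in that direction. A control arm read by the same people would reveal such a shift, but this trial has none.

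Participants and clinicians cannot be masked in a single-arm trial. The laboratory reader can be, without touching care. The main product of this pilot is a descriptive estimate of change, so a biased reading goes straight into what is reported. Once samples have been read unmasked, no analysis can separate the shift from the treatment effect.

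**Working it through.** The protocol states no alpha, power, effect size or reader variability, so there is no planned figure to reproduce. The check is a comparison of sections, followed by an illustration on stated assumptions.

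**1. Which primary readouts are exposed**

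| Readout (section 10) | Reader judgement | Direction predicted | Masking to time point provided |
|---|---|---|---|
| Immunohistochemistry panels | Likely; no scoring rule given | PD-L1 up; p38-MAPK candidates up; for most other markers only some alteration (section 2) | None |
| PD-L1 by immunofluorescence | Likely | Up | None |
| CTC counts and phenotype | Possible; capture is by chip, counting method not stated | More mesenchymal | None |
| NanoString | Little; normalization is automated | p38-MAPK genes up (CTC panel) | Hardly needed |
| T-cell receptor sequencing, flow cytometry | Little | None beyond some alteration | Hardly needed |

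The exposure is confined to the first three rows, and is clearest where a direction is written down.

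**2. What a reading shift does to the estimate**

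Let δ be the true mean change, β the mean shift in the post-SBRT reading caused by expectation, and s the SD of the paired difference. In one arm the mean observed change estimates δ + β, and no second equation separates the two. The standard error of the mean change with n = 10 is s/√10 = 0.316s. Therefore:

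- β = 0.2s is 0.2/0.316 = 0.63 standard errors
- β = 0.5s is 0.5/0.316 = 1.58 standard errors

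More participants would shrink the standard error but leave β unchanged.

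**3. Illustration in counts of participants**

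Assume no true change, normal paired differences and a shift of d = β/s. Each pair then reads as increased with probability p = Φ(d), and

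P(at least 8 of 10 increased) = Σ over k = 8 to 10 of C(10,k) p^k (1−p)^(10−k).

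- d = 0, p = 0.500: (45 + 10 + 1)/1024 = 5.5%
- d = 0.2, p = 0.579: 13.6%
- d = 0.33, p = 0.629: 21.9%
- d = 0.5, p = 0.691: 36.0%

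Setting p directly gives the same picture: 10.0% at 0.55, 16.7% at 0.60 and 38.3% at 0.70.

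The shift sizes are assumptions. The 8-of-10 cut is a way to picture a consistent pattern and is not a rule that the trial uses.

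**The case against.** A reader might infer that the protocol has decided to let assay readers know the time point, or that the primary endpoint as a whole is subjective. The documents support neither.

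- **Reader knowledge is inferred.** In a single-arm trial, the statement that the study is not blinded may describe treatment only. The protocol does not say who reads the assays or what they are told, and coding may already be fixed in the laboratory manual. This stands. However, section 1.4 is unqualified, and the protocol cites the manual only for processing, transfer and specimens.
- **Several readouts are instrument-based.** NanoString, T-cell receptor sequencing and flow cytometry leave little to a reader. This stands and limits the scope.
- **CTC phenotype may be set largely by chip capture.** Section 10 also plans transcriptomic confirmation of the CTC result. This stands as a partial safeguard. It does not cover PD-L1, whose planned confirmation is immunofluorescence, or the p38-MAPK candidates, whose confirmation is immunohistochemistry.
- **Direction is not predicted for most of the immunohistochemistry panel.** Correct. Directional expectation is written for CTC phenotype, PD-L1 and p38-MAPK genes.
- **The size is not known, and no formal test is planned.** Correct. The percentages above are not error rates of this trial. Bias in a descriptive estimate is still bias.
- **Tissue cannot be fully masked.** The pre-SBRT sample is a biopsy and the post-SBRT sample a resection specimen, so a reader may recognize the time point despite a code. Cropped fields help only if an unmasked person does not choose them freely. This stands and shapes the fix.

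**Conclusion.** The point holds in limited form. Section 1.4 declares no blinding and names only consecutive enrolment, which does not protect a before/after reading. The protocol provides no masking to time point for immunohistochemistry scoring, PD-L1 immunofluorescence, or any manual step in CTC counting or PD-L1 reading, although it predicts the direction for CTC phenotype and PD-L1.

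The consequence is a possible bias, of unknown size, in the descriptive estimate of change. Under the assumed shifts it would be 0.6 to 1.6 standard errors of the mean change. This rests on two conditions that the protocol leaves open: that readers can tell the time point, and that a person's judgement enters the reading. It does not show that bias will occur, and it does not reach the instrument-based readouts. The change is worth making because it costs little and has to be in place before samples are read.

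**What to change.** Amend section 1.4 along these lines:

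*Treatment is open label. Blood/CTC samples and immunohistochemistry or immunofluorescence slides or images are labelled with random codes and read by the existing readers without knowledge of time point. The code key is held outside the laboratory, for example by the study coordinator, and released after scores are locked.*

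If the laboratory manual already fixes this, a sentence in section 1.4 citing it is enough.

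Two additions keep the statement honest:

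- Say that masking of tissue is partial, because a core biopsy and a resection specimen look different. If coded fields of view are scored in place of whole slides, they should be chosen by a rule set in advance.
- Say which blood draws form the CTC pair. Section 9.1.1 has one on Day 1 before the first fraction and one before surgery. These carry no such difference in specimen type, so coding should work best there. If live samples cannot wait, stored images can be coded and read later. The protocol does not say whether images are kept, so this needs confirming.

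Cost: coded labels, a key, a short delay before reading, and the step of selecting fields if that option is used. No extra reader, sample or visit is needed, and participant care does not change. The remaining weakness is incomplete masking of tissue.
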